The total number of subjects targeted for randomization will be 318 subjects in Part 1 and 378 subjects in each of Part 2A and Part 2B, with each part having two active treatment groups and a placebo group. There is therefore sufficient power to support the independent analysis of any single study part.

Placebo is used as comparator because there is no approved medication for treatment of hallucinations and delusions in patients with ADP, nor is there any standard of care. Additionally, this study is of short duration, and subjects may be discontinued for lack of efficacy or worsening symptoms.

The study will be randomized with stratification by site, and by whether subjects are living in the wider community or an institution, to balance the number of subjects in the treatment groups and allow fair comparisons within sites and within living situations.

Two assessments of cognition will be used during study drug treatment to monitor any worsening of cognition. Use of the industry standard MMSE will be augmented by use of the DSST, which is more sensitive to slight changes in higher-level cognition than the MMSE.

Two assessments of suicidality will be used in the study: GCAS and C-SSRS. The GCAS will be used because it allows for capture of reports of suicidal behavior in the patient by the study partner or caregiver in subjects with dementia who may not be able to give reliable information in a C-SSRS assessment. The C-SSRS will be used because it allows for mapping to Columbia Classification Algorithm of Suicide Assessment (C-CASA) categories.

In addition to the standard telephone call for safety follow-up at 30 (+4) days after the last dose of study drug (for subjects who discontinue prematurely from the study or do not roll over into the OLE study), a safety follow-up telephone call at 7 (\pm 3) days after the last dose of study drug will occur. This telephone call is timed to detect adverse events (AEs) that might result from having stopped study drug. New and ongoing AEs will be collected.

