For subjects who discontinue prematurely from the study, a telephone call to confirm that the subject is still living will be conducted at 30 (+4) days after the subject's intended day of last dose of study drug (i.e., the day that their last dose of study drug would have been taken had they not discontinued prematurely), and if the subject has died, the cause of death will be sought. Because there may be a lag between an AE leading to discontinuation while taking study drug and death resulting from that event, this assessment is included to ensure that all deaths within the intended period of treatment or 30 days thereafter are taken into account.

1.4.2 **Rationale for Dose Selection**

The proposed doses, 30 mg and 60 mg of ACP-204, have a wide safety margin to no-observedadverse-effect levels in long term preclinical toxicity studies up to 39 weeks. These doses have been well tolerated in a multiple ascending dose study in the elderly and should provide adequate exposure and brain 5-HT_{2A} receptor occupancy. Acadia anticipates that ACP-204 doses of 30 and 60 mg QD may provide exposures associated with an antipsychotic effect. Further, the proposed doses have been shown to be safe and well tolerated in an elderly population.

Dose selection for the current study is guided by ACP-204 PK profile and safety data following the administration of single doses of ACP-204 up to 180 mg in healthy adult subjects and following multiple doses up to 120 mg in healthy adult subjects and 60 mg in healthy elderly subjects, as well as PET study data and nonclinical pharmacology.

The ACP-204 PK profile is linear/dose proportional, with low to moderate variability, with slightly higher exposure in elderly subjects than in younger adult subjects. The ACP-204 half-life (t_{1/2}) is approximately 20 hours, thus establishing once-daily (QD) oral dosing of ACP-204 as an appropriate dosing regimen. In a food-effect study, the criterion for bioequivalence for fed relative to fasted was within the bioequivalence boundary for AUC and C_{max}, and these results indicate that food has no effect on the rate or extent of ACP-204 absorption. ACP-204 was safe and well tolerated over the studied dose range in healthy adult and elderly subjects.

Please refer to the current ACP-204 Investigator's brochure for additional PK and nonclinical pharmacology information.

Benefit/Risk Assessment 1.5

1.5.1 **Known Potential Risks**

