7.3 Time Period and Frequency for Event Assessment and Follow-up

For subjects who roll over into the OLE study, AEs for this study will be recorded from the time informed consent is obtained in this study until the first dose of study drug in the OLE study.

For subjects who discontinue from the study or do not roll over into the OLE, AEs will be recorded from the time informed consent is obtained through the study Safety Follow-up Period.

If an AE is ongoing at the end of the study Safety Follow-up Period, every reasonable attempt should be made to follow and appropriately treat the subject until the AE resolves or until the Investigator deems the AE to be chronic or stable.

In the event that a subject discontinues from the study and has an ongoing AE at the time of discontinuation (Section 4.5.1), the subject should be followed and appropriately treated until the AE resolves or until the Investigator deems the AE to be chronic or stable. If a subject or LAR withdraws consent from the study because of an AE, no additional assessments may be performed (Section 4.4).

For subjects who discontinue from the study and have not withdrawn consent (or had consent withdrawn by LAR) from further data collection, a telephone call to the subject and/or study partner/caregiver to confirm that the subject is still living will be conducted 30 (+4) days after the subject's intended day of last dose of study drug (i.e., the day that their last dose of study drug would have been taken had they not discontinued prematurely). If a subject has died, every effort will be made to collect cause of death information where possible (including documentation; e.g., death certificate or autopsy report with subject identifiers redacted).

7.4 **Reporting Procedures**

7.4.1 **Adverse Event Reporting**

The Investigator must record all observed AEs and all reported AEs. At each visit, the Investigator should ask the subject a nonspecific question (e.g., "Have you noticed anything different since your last visit?") to assess whether any AEs have been experienced since the last report or visit.

Note that any use of medication (and specifically any newly prescribed medication) during the course of a study may indicate the occurrence of an AE that may need to be recorded on both the AE and the concomitant medication page.

Final Version: 2.0

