9.4 Descriptive Statistics

Continuous measurement results will be reported using the number of subjects with data values, mean, standard error of the mean, standard deviation, minimum, maximum, and median. For each categorical outcome, the number and percentage of subjects in each category will be reported.

9.5 **Missing Data**

Handling of missing values will be described in detail in the SAP. Sensitivity analyses will be performed to assess the impact of missing data on the robustness of primary analysis results.

9.6 **Analysis Sets**

Part 1 of Study ACP-204-006 will be locked, unblinded, and analyzed while Part 2A and Part 2B are ongoing.

Part 2A or Part 2B will be analyzed independently from each other and independently from the Part 1 analysis.

The Randomized Analysis Sets of Part 1, Part 2A, and Part 2B include all subjects who were randomized in Part 1, Part 2A, or Part 2B, respectively.

The Randomized Analysis Sets will be used for analyses specified in the SAP based on the randomized treatment assignment.

The Safety Analysis Sets of Part 1, Part 2A, and Part 2B include all randomized subjects in Part 1, Part 2A, or Part 2B, respectively, who received at least one dose of study drug (ACP-204 or placebo). Subjects will be analyzed based on the treatment they actually received.

The Safety Analysis Sets will be used for all safety analyses.

The Full Analysis Sets of Part 1, Part 2A, and Part 2B include all randomized subjects in Part 1, Part 2A, or Part 2B, respectively, who received at least one dose of study drug and who have both a baseline value and at least one post-baseline value for SAPS-H+D total score. Subjects will be analyzed based on their planned randomized treatment.

The Full Analysis Sets will be used for the analysis of all efficacy endpoints.

The PK Analysis Set includes all subjects in the Safety Analysis Set who have sufficient PK data to derive at least one PK parameter.

Any other analysis sets, if necessary, will be defined in the SAP.

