9.8 Safety Analyses

All safety analyses will be performed using the Safety Analysis Set of Part 1 and Safety Analysis Sets of Part 2A and Part 2B, respectively. Safety data collected on or after the first dose of study drug administration up to 30 days after the last dose of study drug, unless specified otherwise, will be summarized by treatment group using descriptive statistics. No formal statistical testing will be performed for any of the safety endpoints.

The safety endpoints are (Section 2.4.1):

- TEAEs
- 12-lead ECGs
- Vital signs, including orthostasis assessment
- Weight and BMI
- Physical examination results
- Clinical laboratory tests
- GCAS score
- C-SSRS
- UKU Sleepiness/Sedation and Orthostatic Dizziness scores
- MMSE score
- DSST score

ESRS-A scores

9.8.1 **Adverse Events**

All AEs will be classified into standard terminology using the Medical Dictionary for Regulatory Activities coding dictionary.

Treatment-emergent adverse events are:

• Any AEs with an onset date of on or after the study drug start date and no later than 30 days after permanent discontinuation of study drug

All AEs will be listed, and TEAEs will be summarized by system organ class and preferred term. Treatment-emergent adverse events, TEAEs leading to discontinuation, TEAEs related to study drug, TEAEs by maximum severity, fatal TEAEs, serious TEAEs, and serious TEAEs related to study drug will all be summarized by treatment group. Adverse events of special interest (AESIs) will be summarized by treatment group as well. Investigator-reported AESIs will populate the primary safety table, and neurologist-evaluated events will be summarized separately in supplemental safety tables in the final study report.

Deaths of subjects who discontinue prematurely from the study that occur between 30 days after the last dose of study drug and 30 days after the subject's intended day of last dose of study drug will be summarized separately.

9.8.2 ECGs, Vital Signs, Weight and BMI, Physical Examination Results, and Clinical **Laboratory Tests**

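### The single TEAE table runs to 30 days after the last dose over all dosed subjects, although rollover subjects are barely observed off drug, so events after stopping appear diluted

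*Protocol*

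**What the plan says.** Section 9.8.1 counts as treatment-emergent any event with an "onset date of on or after the study drug start date and no later than 30 days after permanent discontinuation of study drug". Section 9.8 sets the same horizon for safety data generally, "up to 30 days after the last dose of study drug, unless specified otherwise, will be summarized by treatment group using descriptive statistics", and fixes the population: "All safety analyses will be performed using the Safety Analysis Set of Part 1 and Safety Analysis Sets of Part 2A and Part 2B, respectively". Section 9.6 defines that set as everyone randomised and dosed, with no condition on follow-up. Section 9.4 reports categorical outcomes as number and percentage of subjects.

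Data collection follows another rule. For subjects who roll over, Section 7.3 has adverse events "recorded from the time informed consent is obtained in this study until the first dose of study drug in the OLE study". The note to Figure S-1 and Section 6.7 confine the 7-day and 30-day calls to subjects who discontinue or do not enter the extension. Section 3.1 makes the Week 6 visit the extension's baseline.

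Section 1.4.1 explains the 7-day call: "This telephone call is timed to detect adverse events (AEs) that might result from having stopped study drug".

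**The concern.** The window in the definition is longer than the window observed in some of the subjects counted. A completer who rolls over contributes about 42 days; one who does not contributes about 72. Both count once in the same denominator.

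The loss falls on events after drug is stopped. Those can be seen only in subjects followed off drug, yet Section 9.8.1 pools them with on-treatment events and divides by everyone dosed. Rollover subjects on active drug presumably continue on it, so they are largely not at risk of a withdrawal event and do not belong in that denominator. The trial makes a call to look for such events, but the planned summary does not let a reader see how often they occur.

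There is also a possible problem for the comparison of arms. Rollover and early termination happen after randomisation and may depend on efficacy or tolerability. If they differ by arm, so does the off-drug time behind each percentage.

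**Working it through.** The protocol states no TEAE rate, rollover share or observed-time figure, so there is nothing of its own to reproduce. Rollover shares, event risks and discontinuation patterns below are assumptions.

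**Inputs from the protocol.** Treatment lasts 6 weeks, or 42 days (Section 3.1). Follow-up after the last dose is 30 days (Section 6.7). Arms have 106 subjects in Part 1 and 126 in each of Parts 2A and 2B (Section 9.3).

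**Observed time.** A rollover completer has about 42 days. The gap before the first open-label dose is not stated, but is presumably short because the Week 6 visit is the extension's baseline. A non-rollover completer has 42 + 30 = 72 days. A subject who stops on day t has t + 30.

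**Dilution.** Let q be the 30-day risk of a post-treatment event among subjects followed off drug, and r the share of the arm that rolls over. Over the whole Safety Analysis Set the table shows q × (1 - r). With q = 10%:

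| r (assumed) | Shown | Followed off drug, of 106 | Followed off drug, of 126 |
|---|---|---|---|
| 30% | 7.0% | 74 | 88 |
| 50% | 5.0% | 53 | 63 |
| 70% | 3.0% | 32 | 38 |
| 90% | 1.0% | 11 | 13 |

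With the followed subjects as denominator, the figure is q itself. The direction is certain whenever anyone rolls over.

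**Between arms.** Assume 10% discontinue at a mean of day 21, giving 51 days each. If a share s of completers rolls over, mean observed days = 0.10 × 51 + 0.90 × (42s + 72(1 - s)), and the share followed off drug = 0.10 + 0.90 × (1 - s).

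- s = 70% in both arms: 51.0 against 51.0 days. No imbalance.
- s = 80% against 60%: 48.3 against 53.7 days. The shares followed are 28% and 46%, so an equal 10% post-treatment risk shows as 2.8% against 4.6%.
- Swapping the arms reverses the direction.

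**Effect on the pooled TEAE percentage.** Assume a constant hazard with 10% incidence by day 42. Incidence is then 1 - 0.9^(72/42) = 16.5% by day 72 and 1 - 0.9^(51/42) = 12.0% by day 51.

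- If all non-rollover subjects are observed for 72 days, non-rollover of 20% against 10% gives (0.8 × 10 + 0.2 × 16.5)/(0.9 × 10 + 0.1 × 16.5) = 11.30/10.65, a risk ratio of about 1.06. For 30% against 10% it is 11.95/10.65, about 1.12.
- If they are early terminators observed for 51 days, the ratios are 10.40/10.20, about 1.02, and 10.60/10.20, about 1.04.
- A subject who stops before day 12 has t + 30 < 42, which is less time than a rollover completer. More non-rollover does not always mean more observed time.

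**The case against.** The strongest reply is that additional tables are SAP content. Section 9 sends detailed methods to a separate SAP for each part, and the safety window in Section 9.8 applies unless otherwise specified, so nothing forbids a split by period. That is fair, and the unseen SAPs may contain it. But the window and the analysis set are fixed in Sections 9.8 and 9.8.1, and the mismatch with Section 7.3 arises there.

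It can also be said that the TEAE percentage is not offered as a withdrawal risk, that all events are still recorded and listed, and that no formal safety testing is planned. The first two stand: detection is not impaired, only the reading of frequency. The third gives little comfort, because descriptive percentages then carry the comparison.

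Three stronger readings are tempting, and the protocol does not support them:

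- A reader might infer that the arms are compared over unequal time. That follows only if rollover or discontinuation differs by arm. A wholly inert drug would produce no such difference beyond chance.
- A reader might infer that Section 1.4.1 makes a false promise about deaths, since it says "this assessment is included to ensure that all deaths within the intended period of treatment or 30 days thereafter are taken into account". That paragraph concerns subjects who discontinue prematurely and promises nothing about rollover completers. Section 9.8.1 already summarises fatal TEAEs, and separately the later deaths of early terminators.
- A reader might conclude that the main window should end at the last dose. That is a debatable trade: early terminators would then have only t days against 42, and events soon after stopping would leave the main comparison.

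**Conclusion.** The mismatch is real and worth a modest change. In the pooled table, events after the last dose appear at (1 - r) times their frequency among subjects followed off drug: 5% to 1% for a 10% risk if r is 50% to 90%. This rests on an assumed r, on little off-drug time before the first open-label dose, and on follow-up being completed in subjects who do not roll over.

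Bias between arms is conditional, with size and direction unknown. Under the constant-hazard illustration, pooled risk ratios run from about 1.02 to 1.12, depending on how far non-rollover differs and on whether those subjects are early terminators or completers. On-treatment events over the six weeks are not affected by the rollover cut-off.

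**What to change.** Keep the 30-day TEAE table and add to Section 9.8.1:

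1. a by-arm summary of TEAEs with onset up to the last double-blind dose;
2. a separate by-arm table of events with onset after the last double-blind dose, with the number of subjects who entered Safety Follow-up as denominator;
3. the rollover share and observed time in each arm, so that a reader can judge whether the pooled percentages are comparable.

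This uses data already collected and changes no procedure. It costs one or two extra tables. The follow-up table will have a smaller denominator (about 32 of 106 or 38 of 126 per arm if 70% roll over). Those subjects are selected after randomisation, so the table should be read as descriptive.

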9.8.3 GCAS, C-SSRS, UKU Sleepiness/Sedation and Orthostatic Dizziness, MMSE, **DSST**, and ESRS-A

UKU Sleepiness/Sedation and Orthostatic Dizziness, MMSE, DSST, and ESRS-A scores and changes from Baseline will be summarized by treatment group and visit and will be analyzed using an MMRM model similar to the primary analysis. For the GCAS, the number and

Final Version: 2.0

Study: ACP-204-006 Final Version: 2.0 Clinical Study Protocol Amendment 3 Date: 15 October 2024

percentage of subjects with a score of 3 or 4 during the study will be tabulated. For the C-SSRS, the summary descriptive statistics will be tabulated.

9.9 Pharmacokinetic and Pharmacokinetic/Pharmacodynamic Analyses

The PK and PK/PD endpoints are ACP-204 PK parameters using a population PK approach and PK/PD of ACP-204 using appropriate PK/PD analysis methods.

Plasma concentration data for ACP-204 will be listed and summarized using descriptive statistics. Results will be used for other analyses (e.g., population PK and PK/PD modeling), which will be presented in a separate report(s). ACP-204 metabolites will be summarized where appropriate.

Guided by exploratory analyses, PK/PD models to describe the exposure-response relationship between ACP-204 exposure parameters and the relevant efficacy and safety endpoints will be developed using appropriate PK/PD methods. Results will be presented in a separate report per a prespecified data analysis plan.

ACP-204 plasma concentration data will remain blinded until unblinding of the clinical database for each respective part of the study.

9.10 Subgroup Analyses

Selected analyses may be performed in subgroups defined in the SAP.

9.11 Interim Analyses

No interim analyses are planned for this study. The planned analysis for Part 1 is not considered an interim analysis. It will occur only after all subject participation in Part 1 is complete.

9.12 Data and Safety Monitoring Board

An external DSMB will review interim safety data, including data on AEs, SAEs, and safety laboratory data. The DSMB will be independent of the Sponsor and the Investigators and will be empowered to recommend whether the study should be terminated due to safety concerns, continue as planned, or continue with modification.

The DSMB may review blinded, unblinded, or partially unblinded data, but the Sponsor and the Investigators will remain blinded to the data provided to the DSMB until the official unblinding of the databases. In cases where the DSMB reviews unblinded data, the treatment codes will be released to an independent statistician/programmer to produce unblinded statistical outputs provided only to the DSMB.

The DSMB membership, activities, responsibilities, and frequency of meetings will be described separately in the DSMB charter.

While the DSMB will be making recommendations regarding future conduct of the study, the Sponsor retains final decision-making authority on all aspects of the study.

10 STUDY MANAGEMENT AND DATA COLLECTION

10.1 Data Collection and Management Responsibilities

All documents required for the conduct of the study as specified in the ICH E6 (GCP) guidelines will be maintained by the Investigator in an orderly manner and made available for monitoring and/or auditing by the Sponsor and regulatory authorities.

To safeguard data integrity, the Investigator, site staff, and service providers delegated by the Investigator/institution must follow the "ALCOA+" principles, ensuring that data should be "Attributable, Legible, Contemporaneous, Original, and Accurate." The "+" indicates that data is also "Complete, Consistent, Enduring, and Available."

The Investigator and institution must permit authorized representatives of the Sponsor or designees (including monitors and auditors), regulatory authorities (including inspectors), and the IRB/EC direct access to source documents (such as original medical records, both in paper format and in electronic systems, where applicable) as allowed by local regulations. Direct access includes permission to examine, analyze, verify, and reproduce any records and reports that are needed for the evaluation of the study, either in person or through remote video/electronic medium (such as email) if applicable. The Investigator must ensure the reliability and availability of source documents from which the information on the eCRF was derived.

10.2 Source Documents

All study specific information obtained at each study visit must be recorded in the subject's record (source documentation), and then entered into a validated EDC database by trained site personnel and/or transferred electronically into EDC or another secure data repository. The source documentation may consist of source notes captured by site personnel, as well as laboratory reports, ECG reports, electronic source data, electronic clinical outcomes assessments, and rating scales platforms.

